## 10 ADVERSE EVENT REPORTING

At each study visit, patients will be evaluated for new AEs and the status of existing AEs. The Investigator may elicit symptoms using an open-ended question, followed by appropriate questions that clarify the patient's verbatim description of AEs or change in concomitant medications. Adverse events will be collected from the time of signing of the informed consent through Visit 2. Additional AEs/SAEs assessed as related to the study drug or study procedures that occur during the 30-day follow-up period will be collected in the clinical database.

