### **6.2 Study Design**

This is a prospective, open-label, multicenter study of patients with Pompe disease who are naïve to treatment with alglucosidase alfa or who have been previously treated with alglucosidase alfa for at least 6 months. The patient or the patient's legal guardian(s) must provide informed consent prior to performing any protocol-related procedure. Eligible patients will receive one IV infusion of alglucosidase alfa 20 mg/kg body weight at visit 2 (Day 1).

Approximately 20 patients (10 patients <18 years old and 10 patients ≥18 years old) with Pompe disease who have confirmed GAA enzyme deficiency from skin, blood, or muscle tissue and/or 2 confirmed GAA gene mutations who meet all other eligibility criteria as outlined in [Section 7](#) will be enrolled in the study. Patients will be monitored for adverse events (AEs) for a minimum of 2 hours after infusion.

Alglucosidase alfa will be administered by IV infusion at a dose of 20 mg/kg body weight as outlined in [Section 8](#). Prior to the infusion, the patient should be assessed by the Investigator or appropriate designee to determine if the patient is free of acute illness and is clinically stable to receive the infusion.

Pharmacokinetic (PK) and safety assessments will be performed at the scheduled visit. Adverse events and concomitant medications/therapies will be monitored continuously throughout the study. Patients who are withdrawn from the study will not be replaced (ie, a patient's study number will not be reused); however, additional patients may be enrolled to offset patient dropouts.

Patients who complete or withdraw from the study will have a follow-up assessment performed 30 days following their administration of investigational product for all ongoing AEs at the time of administration of investigational product. All serious adverse events (SAEs) ongoing at time of administration of investigational product should be followed up until resolution.

An independent Data and Safety Monitoring Board (DSMB) will perform ad hoc reviews of safety data as outlined in the DSMB Charter, which is maintained separately from the study protocol. An immunologist will be consulted, when necessary, to review information and provide treatment recommendations for infusion-associated reactions (IARs).

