### 10.3.2 Adverse Events Occurring After Study Treatment

Adverse events will be collected from the time of the patient's first receipt of investigational product until the patient completes the study or terminates from the study.

Serious AEs will be collected from the time of the patient's first receipt of investigational product until the patient completes the study or terminates from the study.

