### **10.3.3 Adverse Events Occurring Following Patient Discontinuation of Treatment**

For patients who prematurely discontinue study treatment (see [Section 8.3.3](#)), but who are not withdrawn from the study, AEs will continue to be recorded until the patient completes the study (see [Section 6.2.1.1](#) for definition of patient completion). See [Section 10.3.4](#) for reporting requirements after the patient completes the study.

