## **10.4 Recording of Adverse Events/Serious Adverse Events**

All AEs/SAEs experienced by the patient will be recorded on the eCRF. Information including a concise description of the event; date and time of event onset and resolution; determination of seriousness, severity, corrective treatment, outcome, relationship to investigational product; and action taken regarding the investigational product will be recorded. Vital signs, laboratory results, and other safety assessments noted in [Section 9.4](#) will be recorded, if they meet the definition of an AE (see [Section 10.1.1](#)). When possible, a diagnosis should be recorded as an AE, rather than symptoms or isolated laboratory abnormalities related to that diagnosis. A medical or surgical procedure is not an AE; rather the condition leading to the procedure should be recorded as the AE. If the condition is not known, the procedure must be reported as an AE instead. Similarly, death is not an AE, but is rather the outcome of the AE(s) that resulted in death. If the AE(s) leading to death are not known, then death must be reported as an AE.

All SAEs experienced by the patient will be recorded on an SAE Report Form and reported to the Sponsor according to [Section 10.5](#).

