## **10.6 Follow Up of Adverse Events/Serious Adverse Events**

All AEs/SAEs documented at a previous visit/contact that are designated as ongoing will be reviewed by the Investigator at subsequent visits/contacts.

The Investigator will provide follow-up information for any SAE to the Sponsor's GPE department, as soon as it is available. The Sponsor or regulatory authorities may request additional information regarding an SAE.

All AEs will be followed until resolution or study termination. Serious AEs will be followed until resolution, the condition stabilizes, or the Investigator and Sponsor agree that follow up is no longer necessary. Rules for AE/SAE follow up apply to all patients, including those withdrawn prematurely to the extent allowed by the patient's consent. The Investigator will ensure that follow up includes further investigations consistent with appropriate medical management and patient consent to elucidate the nature and/or causality of the AE/SAE.

For the purposes of the study, status of ongoing and new AEs/SAEs will be assessed 30 days after the patient's administration of investigational product. Any new AE or SAE that occurs during the 30-day follow-up period and prior to initiation of commercial therapy and is assessed as related to the drug or study procedures will be reported/collected in the clinical database. All AEs will continue to be followed until the 30-day assessment. Ongoing SAEs at the 30-day follow-up assessment will need to be further followed until resolution, until the Investigator deems follow up is no longer medically necessary or until the patient is lost to follow up. Adverse events and SAEs reported after the initiation of commercial product will be considered spontaneous reports for the purposes of regulatory reporting. Refer to the SOM for details of this assessment.

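### After Visit 2, Protocol 10 and 10.6 collect only related new AEs, while 10.3.2, 10.3.3, 10.4 and the SAP collect all AEs, so the all-causality TEAE tables can be incomplete

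*Protocol*

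**What the plan says.** **Related-only after Visit 2.** Protocol 10 (Adverse Event Reporting) states: "Adverse events will be collected from the time of signing of the informed consent through Visit 2". For the clinical database it then adds: "Additional AEs/SAEs assessed as related to the study drug or study procedures that occur during the 30-day follow-up period will be collected". Protocol 10.6 gives the same rule on relatedness to drug or procedures, with an extra limit, for what enters the clinical database: "Any new AE or SAE that occurs during the 30-day follow-up period and prior to initiation of commercial therapy and is assessed as related".

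**All AEs to study completion.** Protocol 10.3.2 collects AEs from "first receipt of investigational product until the patient completes the study or terminates from the study". Protocol 10.3.3 covers patients who stop treatment "but who are not withdrawn from the study, AEs will continue to be recorded until the patient completes the study". Protocol 10.4 says: "All AEs/SAEs experienced by the patient will be recorded on the eCRF". SAP 2.1.4.1 likewise records AEs from consent to the end of the study. Under Protocol 6.2.1.1 a patient completes when the Week 4 call has taken place, and Appendix A puts that call at least 30 days after dosing.

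**What is tabulated.** SAP 2.4.5.1 plans tables of all TEAEs and of serious TEAEs by SOC and PT, with no restriction on causality. Protocol 12.8.3 tabulates treatment-emergent events by four relationship categories, two of which are not related and unlikely related.

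**The concern.** Protocol 10 and 10.6 give sites one rule for new events after Visit 2, and 10.3.2, 10.3.3 and 10.4 give them another. A site could leave an unrelated late event out under the first or enter it under the second, and cite the protocol either way.

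The planned tables assume the second rule. Under the first, a table labelled as all TEAEs would hold every event up to Visit 2 and only related events afterwards. The any-TEAE and serious-TEAE rows, and the two unrelated categories in Protocol 12.8.3, could then be too low. Nothing in the output would show it.

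Protocol 10.6 also differs from section 10. Under its commercial-therapy limit, even related events would be left out once commercial treatment begins. Neither Protocol 10.3.2 nor the SAP has such a limit.

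**Working it through.** The plan states no figure to reproduce, so the main check is a comparison of the texts.

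| Source | New events after Visit 2 | Until |
|---|---|---|
| Protocol 10 | related to drug or procedures only | 30-day follow-up |
| Protocol 10.6 | related only | 30-day follow-up, and before commercial therapy |
| Protocol 10.3.2 | all | completion or termination |
| Protocol 10.3.3 (off treatment, still in study) | all | completion |
| Protocol 10.4 | all, on the eCRF | no limit stated |
| SAP 2.1.4.1 | all | end of the study |
| SAP 2.4.5.1 tables | no relatedness filter | not stated in the table list |

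The first two rows cannot be met together with the next four for an unrelated event that starts after Visit 2. SAP 1.5 and 1.6 record no modification that settles the matter.

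**How much of the window the related-only rule covers**
- Minimum window, from the call at 30 days or later: 30 × 24 = 720 h.
- Infusion length: Protocol 8.1 says about 4 h. The recommended steps agree: half an hour at each of 1, 3 and 5 mg/kg/hr delivers 4.5 mg/kg in 1.5 h, and the remaining 15.5 mg/kg at 7 mg/kg/hr takes 2.2 h, 3.7 h in all.
- Earliest end of Visit 2: 4 h infusion + 2 h observation (Protocol 8.1) = 6 h.
- Latest end: 4 h + last PK sample at 24 h after infusion (Protocol 9.5) = 28 h.
- Share under the related-only rule: (720 − 6)/720 = 714/720 = 99%; (720 − 28)/720 = 692/720 = 96%.

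These are shares of time, not of events.

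**What one patient is worth.** The tables count patients. With about 20 treated (Protocol 12.2), a patient whose only TEAE is an unrelated one starting after Visit 2 lowers the any-TEAE row by 1/20 = 5 percentage points.

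**Range under an assumed rate.** Let *p* be the proportion of patients with a new unrelated AE after Visit 2. The documents give no value.

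| Assumed *p* | Expected patients, 20*p* | Chance of at least one, 1 − (1 − *p*)^20 |
|---|---|---|
| 5% | 1 | 64% |
| 10% | 2 | 88% |
| 20% | 4 | 99% |
| 50% | 10 | over 99% |

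The expected counts are upper limits for the loss in the any-TEAE row, because a patient with another collected TEAE still counts there.

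**The case against.** The case for leaving this alone is that little depends on it. Protocol 6.1.2 says routine safety assessments are not endpoints, 12.1 rules out formal inference, and each patient receives one infusion of the approved dose. Protocol 10.5 sends every SAE to pharmacovigilance whatever its cause, so what the tables lose is mainly unrelated, non-serious, late events. Protocol 10.6 refers to the Study Operations Manual for details of the 30-day assessment. That manual is not among the documents and may give sites a single instruction. All of this stands and limits the impact. It does not reconcile the protocol text. Sections 10 and 10.6 also restrict which new SAEs enter the clinical database, so the serious-TEAE table could disagree with pharmacovigilance. That sites will in fact diverge is an inference.

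A reader might go further in four ways that the documents do not support.

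- **Protocol 6.2 as a third collection rule.** It provides for a "follow-up assessment performed 30 days following their administration of investigational product for all ongoing AEs at the time of administration of investigational product". This concerns follow-up of ongoing events and does not exclude new ones; the same section has AEs monitored continuously.
- **An undefined TEAE period that undermines the abnormality summaries.** The SAP never defines that label, but the after-treatment epoch in 2.1.4 and the TEAE definition in 2.1.4.1 supply the substance. Laboratory tests are scheduled only at Screening, and ECG and vital signs only at Visit 2. The end of the period therefore matters only for unscheduled tests and for AEs with incomplete onset dates.
- **Commercial therapy as the end of the TEAE period.** No SAP section says so; Protocol 10.6 uses it only to limit collection. The documents do not say when patients start or resume commercial treatment, so the share of the window lost cannot be calculated.
- **Related as excluding possibly related.** Protocol 10.1.3.1 and 10.3.4 name both categories, while 10 and 10.6 say only related. The text does not settle which is meant, and this point does not rely on the narrower reading.

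**Conclusion.** The contradiction is real, lies in current text, and should be fixed. Under Protocol 10 and 10.6, unrelated events that start after Visit 2 stay out of the clinical database, and under 10.6 so do related events after commercial therapy starts. The all-TEAE and serious-TEAE tables can then be too low for patients with any TEAE or an unrelated one. If sites follow 10.3.2, 10.3.3 and 10.4 instead, nothing is lost.

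The size of the under-count cannot be derived. The documents support only the reach of the rule (96% to 99% of the minimum 30 days, taking Visit 2 to end between 6 and 28 h after infusion start) and the weight of one patient (up to 5 percentage points, assuming 20 treated). The expected counts of 1 to 10 patients rest on assumed rates. Counts of patients with a related TEAE before commercial therapy are unaffected if related is read to include possibly related. The primary PK objective and the antibody analysis are untouched.

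**What to change.** Reconcile Protocol 10, 10.3.2, 10.3.3, 10.4 and 10.6 to one AE collection rule.

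- **Preferred:** collect all AEs, whatever their relationship, from consent to the follow-up call. This matches SAP 2.1.4.1, the SAP tables and the 30-day safety assessment in Protocol 9.4. It adds entries but no contacts, because 10.6 already provides that "status of ongoing and new AEs/SAEs will be assessed 30 days after" dosing.
- **If related-only follow-up is kept:** label the SAP TEAE tables as all-causality through Visit 2 and related-only afterwards.
- **In either case:** state whether the commercial-therapy limit in 10.6 applies, and make the SAP agree.

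Two minor terminology edits can go with this. State in SAP 2.1.4 that the treatment-emergent adverse event period is the after-treatment epoch. Define or delete the posttreatment period that SAP 2.1.2 attributes to 2.1.4.

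The cost is a wording amendment with IRB/IEC approval (Protocol 13.4), a short SAP edit and, under the preferred rule, some additional unrelated AE entries.

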### 10.1 Definitions

#### 10.1.1 Definition of an Adverse Event

An AE is any untoward medical occurrence in a clinical investigation patient, which does not necessarily have a causal relationship with the investigational product (active or placebo drug, biologic, or device). An AE can, therefore, be any unfavorable and unintended symptom, sign, disease or condition, or test abnormality whether or not considered related to the investigational product.

Adverse events include:

- Symptoms described by the patient or signs observed by the Investigator or medical staff.
- Test abnormalities (laboratory tests, ECG, X-rays, etc.) that result in an alteration in medical care (diagnostic or therapeutic).

Abnormalities present at baseline are considered AEs only if they reoccur after resolution or they worsen during the study.

#### 10.1.2 Definition of a Serious Adverse Event

An SAE is any AE that results in any of the following:

Death: The patient died as the result of the event.

Life-threatening event: Any AE that places the patient, in the view of the Investigator, at immediate risk of death from the AE as it occurred, i.e., does not include an AE that had it occurred in a more severe form, might have caused death.

Required or prolonged inpatient hospitalization: The AE resulted in an initial inpatient hospitalization or prolonged an existing hospitalization of the patient. If a patient is hospitalized as part of the clinical use of the product, a period of normal hospitalization will be outlined in the protocol or by the judgment of the Investigator. Hospitalizations longer than this period will be prolonged hospitalizations.

Persistent or significant disability/incapacity: An AE that results in a substantial disruption of a person's ability to conduct normal life functions.

Congenital anomaly/birth defect: A congenital anomaly/birth defect that occurs in the offspring of a patient exposed to the investigational product.

Important medical events: An AE that may not result in death, be life-threatening, or require hospitalization may be considered an SAE when, based upon appropriate medical judgment, the event may jeopardize the patient or subject and may require medical or surgical intervention to prevent one of the outcomes listed above.

For this particular protocol, due to the medical significance of any new ventilator use in this patient population, any new use of invasive ventilatory support (not including planned surgical procedures, if total duration of ventilatory support is less than 3 days) will be considered an important medical event and will be reported as an SAE. If a patient requiring ventilatory support becomes ventilator independent, the next instance of invasive ventilatory support (if applicable) will be considered a new SAE.

### **10.1.3 Additional Definitions with Relevance to Safety Reporting**

#### **10.1.3.1 Product Administration-Associated Reactions or Events**

IARs are defined as adverse events that occur during either the infusion or the observation period following the infusion which are deemed to be related or possibly related to study drug. At the discretion of the Investigator, adverse events occurring after completion of the post-infusion observation period that are assessed as related may also be considered IARs.

These events should be reported to the Sponsor's GPE department within 24 hours of the Investigator's first knowledge of the event. Refer to [Section 9.4.6.3](#) for additional testing in the event a patient experiences a moderate, severe, or recurrent IAR suggestive of hypersensitivity reactions. Suggested guidelines for the management and reporting of IARs are summarized in the SOM.

## **10.2 Evaluation of Adverse Events/Serious Adverse Events**

### **10.2.1 Relationship to Study Treatment**

Assessment of the association between the AE and study exposure is important for regulatory reporting. This assessment is to be made in blinded studies and also for known comparators. For each AE/SAE the Investigator determines whether there is a reasonable possibility that the AE may have been caused by the study treatment according to the categories below:

- Not Related: There is no suspicion of a causal relationship between exposure and the AE.
- Unlikely Related: There is no evidence for a causal relationship between exposure and the AE; however, such a relationship cannot be ruled out.
- Possibly Related: There is some evidence supporting the possibility of a causal relationship between exposure and the AE.
- Related: There is strong evidence that there is a causal relationship between exposure and the AE.

A relationship to the investigational product must be given for each AE/SAE recorded, even if there is only limited information at the time.

The Investigator may change his/her opinion of causality in light of follow-up information, amending the AE/SAE report accordingly.

### **10.2.2 Relationship to Study Procedures**

Relationship to study procedures will be recorded on the eCRF.

SAEs that are attributed to a study procedure should have that information explicitly included in the narrative.

### **10.2.3 Severity Grading of Adverse Event Scoring**

Note that this is not the same as “seriousness,” which is defined in [Section 10.1.2](#). Seriousness serves as a guide for defining regulatory reporting obligations.

### **Severity Grading**

The Investigator will assess the severity of all AEs/SAEs as Mild, Moderate, or Severe, based on the following definitions (developed from Clinical Data Interchange Standards Consortium Study Data Tabulation Model standard terminology v3.1.1).

#### **Definitions:**

Mild: A type of AE that is usually transient and may require only minimal treatment or therapeutic intervention. The event does not generally interfere with usual activities of daily living.

Moderate: A type of AE that is usually alleviated with additional specific therapeutic intervention. The event interferes with usual activities of daily living, causing discomfort, but poses no significant or permanent risk of harm to the research participant.

Severe: A type of AE that interrupts usual activities of daily living, or significantly affects clinical status, or may require intensive therapeutic intervention.

### **10.2.4 Outcome**

Outcome describes the status of the AE.

The Investigator will provide information regarding the patient outcome of each AE.

**Definitions** for possible results of an AE outcome:

- Fatal: The termination of life as a result of an AE.
- Not recovered/not resolved: The patient has not recuperated or the AE has not improved.
- Recovering/resolving: The patient is recuperating or the AE is improving.
- Recovered/resolved: The patient has recuperated or the AE has resolved.
- Recovered with sequelae/resolved with sequelae: The AE has resolved, but the patient has been left with symptoms or pathology.
- Unknown: Not known, not observed, not recorded, or refused.

## 10.2.5 Action Taken Regarding the Investigational Product

The Investigator will be required to provide the action taken regarding investigational product (eg, active, comparator) in response to the AE.

Options include:

- Dose increased: Increase in the frequency, strength or amount of investigational product administered.
- Dose not changed: No change in administration of the investigational product.
- Dose reduced: Reduction in the frequency, strength or amount of investigational product administered.
- Drug (investigational product) interrupted: Temporary interruption (termination) in administration of the investigational product.
- Drug (investigational product) withdrawn: Administration of the investigational product terminated (no further dosing).
- Not applicable: Determination of a value is not relevant in the current context.
- Unknown: Not known, not observed, not recorded, or refused.

## 10.3 Timeframe for Collection of Adverse Events/Serious Adverse Events

### 10.3.1 Adverse Events Occurring Prior to Study Treatment

Adverse events will be collected from the time of signing of the written informed consent until the patient's first receipt of investigational product.

Serious AEs will be collected from the time of signing of the written informed consent until the patient's first receipt of investigational product.

